Participants: Participants will be physically healthy adults (1:1 gender ratio) (age 18 – 55) who meet DSM-5 criteria for PTSD⁵⁷ with index trauma exposure within the previous 5 years. Justifications for this include a greater likelihood of remembering the details of the event and our prior finding indicating changes in sleep characteristics over the duration of PTSD.⁵⁸ Exclusion criteria include: 1) medical or psychiatric conditions that require consistent use of medication, except for hormonal contraceptives; 2) medical condition that affects sleep; 3) inability to remember most details of the index event; 4) body mass index ≥ 40 (due to very high comorbidity rates of sleep apnea⁵⁹); 5) diagnosis of a sleep disorder other than insomnia including PSG findings of apnea/hypopnea index $> 10/\text{hour}$; 6) consumption of more caffeine than 5 cups of coffee/day equivalent; 7) smoking > 20 cigarettes/day; 8) habitual bedtimes after 2AM, habitual rise times after 9AM, or habitual napping > 1 hour/day; 9) moderate or severe alcohol or drug use disorders within the past year; 10) positive urine toxicology for illicit drugs including cannabis; 11) a diagnosis of psychotic disorders, bipolar disorder, or depression that preceded the onset of PTSD; 12) suicidal ideation with intent to act or with specific plan and intent in the past 6 months [Type 4 – 5 ideation on the Columbia Suicide Severity Rating Scale (C-SSRS)] or history of a suicide attempt; 13) completion of exposure-based therapy targeting the index trauma; 14) pregnancy or breast feeding (All female participants will be required to complete an urine pregnancy test. Sexually active female participants will be required to use a medically acceptable form of birth control); 15) known sensitivity or allergy to an orexin receptor antagonist; and 16) limited ability to read or write English.

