Design and Overview (Table 3): This is a randomized, double-blind, placebo-controlled trial examining the effects of suvorexant (Merck & Co., Kenilworth, NJ), a dual orexin receptor antagonist that is FDA approved for insomnia, on sleep and PTSD symptom reduction following WNE. We will employ our successful recruitment strategies, including flyers, outreach activities, and referral from previous participants. Potential participants will initially be screened over the phone or in person, and those who meet initial criteria will be invited to the Clinical Research Unit (CRU) at Howard University to complete a consent procedure, questionnaires, a clinical interview, a physical examination, and urine tests. Participants who meet the selection criteria will be invited to complete two pairs of 30-minute WNE sessions and four overnight PSG recordings [screening, baseline, between WNE sessions (twice)]. Both pairs of WNE sessions will occur at 8PM and 8AM in the following morning with intervening sleep. The second pair will occur one week after the first pair. Four WNE sessions are

Table 3. Study Design

Day	1	2	3	4	5	11	12	18
Consent; Questionnaires	X							
Physical exam	X							
Vital signs	X				X		X	
Urine tests	X							
CAPS (lifetime & past month)	X							
SCID	X							
CAPS (past week)				X	X		X	
C-SSRS	X			X	X		X	
Alertness scale				X	X		X	
Adverse event assessment	X			X	X	X	X	
WNE (AM)					X		X	
WNE (PM)					X		X	
Suvorexant or placebo					X		X	
PSG		X screen	X baseline		X		X	

needed because the majority of participants in the preliminary study did not achieve remission until after completing the second pair of WNE. Participants will be stratified by gender and randomly assigned to either suvorexant or placebo. After the 1st evening WNE, a 10 mg tablet of suvorexant or placebo will be administered orally 30 minutes before bedtime. If the medication is well tolerated, the dose will be increased to 20 mg at the 2nd administration after the 3rd WNE. The recommended dose is 10mg, and the maximum recommended dose is 20mg.⁶⁰ The 1-week CAPS will be administered before the 1st and 3rd sessions and at 1-week follow-up.

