Study Medication Administration: Participants will be stratified for gender and randomly assigned to either suvorexant or placebo before the 1st WNE. Suvorexant or placebo will be administered orally after the 1st and 3rd WNE, 30 minutes before the participant's habitual bedtime. If the participant well tolerates 10mg, the dose will be increased to 20mg at the 2nd administration. Participants will have continuous access to research nurses during the sleep recording. In the following morning, a nurse will assess possible adverse effects.

Written Narrative Exposure (WNE): We will use a procedure similar to the one used in the R21 study. Sessions will begin at 8PM and approximately 8AM. The morning sessions will not start until the participant's alertness level reaches the level he/she indicated in the morning after the baseline PSG recording. The participant will sit at a desk in a private room with a facilitator, and a pulse transducer will be attached to the distal of the middle finger of his/her non-dominant hand placed on the desk. After a 10-minute acclimatization period, a 5-minute baseline pulse recording will begin. At the end of the baseline, the facilitator will provide instructions to write in as much detail as possible about his/her index trauma including what

happened, how s/he felt, and what s/he perceived and thought and to use the entire 30 minutes. The facilitator will also instruct the participant to orally report an overall level of distress on a scale from 0 – 100 [subjective units of distress scale (SUDS)] at baseline, every 10 minutes, and at the end of the writing period. The facilitator will remain in the same room during the writing to obtain SUDS scores and to assist and encourage the participant if necessary. At the end of the writing period, if warranted, the facilitator will instruct the participant in relaxation techniques for ≤10 minutes. Participants will not be dismissed until distress is minimal.

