Statistical Analysis Plan

Official Title: Can Blocking the Orexin System Enhance Sleep's Benefits to Therapeutic Exposure for PTSD?

NCT number: NCT02849548

Date of the Document: July 7,2016

Data Analysis Plan: Initially, data will be pre-screened for errors, outliers, normality of distributions, and any necessary modifications such as transformation will then be conducted. The suvorexant and placebo groups will be compared on demographics and baseline measures using *t*-tests or chi-squared tests to examine group comparability. Fig. 1 describes each hypothesis. **Hypothesis 1a:** The primary comparison will be between the 2 groups (suvorexant vs. placebo) and sleep parameters measured at 3 time points (baseline, post-Session 1, and post-Session 3). A repeated-measures ANOVA will be performed to examine whether there is a Group x Time interaction effect on each sleep parameter of interest (i.e., N3, WASO, and REM sleep). If a significant interaction effect is found, group comparisons will be performed at each time point. **Hypothesis 1b:** A repeated-measures ANOVA will be performed to examine whether there is a Group x Time interaction effect on CAPS scores. In addition, 2(Group) x 2(Time) ANOVAs will be performed to examine if there is an interaction effect on intersession habituation between Session 1 & 2 and between Session 3 & 4, using a baseline-corrected highest average pulse rate as a dependent variable. **Hypothesis 1c:** To examine indirect effects of suvorexant on PTSD through the mediator, post-WNE sleep change, a path analysis using bootstrapping procedures will be performed for each sleep parameter of interest using SPSS macros developed by Preacher & Hayes.⁷⁰ Baseline CAPS scores will be included as a covariate. The same method will be used to examine indirect effects of suvorexant on intersession habituation.

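### Randomisation is stratified by gender but no outcome analysis includes it; if gender predicts the tested contrast, tests are somewhat conservative and intervals somewhat too wide

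*SAP*

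**What the plan says.** The Protocol states the stratification twice. Under Design and Overview: "Participants will be stratified by gender and randomly assigned to either suvorexant or placebo". Under Study Medication Administration: "Participants will be stratified for gender and randomly assigned to either suvorexant or placebo before the 1st WNE". The Participants section also plans equal numbers of men and women. Neither statement says how balance within gender is to be achieved, for example by blocks.

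The SAP's Data Analysis Plan does not carry gender into any outcome analysis:

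- **Hypothesis 1a (sleep):** "A repeated-measures ANOVA will be performed to examine whether there is a Group x Time interaction effect on each sleep parameter of interest". This is followed by between-group tests: "If a significant interaction effect is found, group comparisons will be performed at each time point".
- **Hypothesis 1b (CAPS):** "A repeated-measures ANOVA will be performed to examine whether there is a Group x Time interaction effect on CAPS scores". Pulse is analysed by 2 x 2 Group by Time ANOVAs.
- **Hypothesis 1c:** bootstrap path models with baseline CAPS as the only named covariate.

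The nearest the SAP comes to gender is the initial check that the arms "will be compared on demographics and baseline measures". That is not an outcome analysis.

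**The concern.** When randomisation forces the arms to have the same gender mix, gender can no longer contribute to the difference between arms. An analysis that leaves gender out still counts the gender variation in its error term. The standard error then overstates the true uncertainty, so tests reject less often than 5% under the null and confidence intervals are wider than they need be.

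What is at stake is precision, in a trial that expects 54 completers. Nothing here biases the treatment effect or inflates false positives when balance is enforced.

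**Working it through.** **Inputs.** From the SAP (Power considerations): alpha .05; 54 completers, 27 per arm. From the Protocol: equal numbers of men and women; stratification by gender; about 70 completing the first two sessions and 54 completing everything (Feasibility). The documents give no figure for how far gender predicts sleep, CAPS or pulse, or change in them, so there is no figure of the plan's own to reproduce. All gender effects below are assumptions, as is the correlation of 0.5 between repeated measures. The SAP states no correlation. Its 12 participants for CAPS at f = 0.40 reproduce with three time points and 0.5, but its 16, 22 and 50 for sleep do not all do so. This point does not rest on those sample sizes.

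**Step 1: type I error and interval width.** Let R² be the share of variance in the analysed contrast explained by gender. Under balance the true variance of the arm difference is proportional to 1 − R², while the unadjusted analysis uses 1. Hence, in large samples:

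- actual size = 2 × [1 − Φ(1.96/√(1 − R²))]
- interval width relative to the correct width = 1/√(1 − R²)

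| R² | 1.96/√(1 − R²) | Actual size | Width ratio |
|---|---|---|---|
| 0 | 1.960 | 5.0% | 1.00 |
| 0.05 | 2.011 | 4.4% | 1.03 |
| 0.10 | 2.066 | 3.9% | 1.05 |
| 0.25 | 2.263 | 2.4% | 1.15 |

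**Step 2: which gender association matters.** Trials were simulated with 54 participants, 27 men and 27 women balanced across arms, and three time points (20,000 runs under the null, Monte Carlo error about 0.15 points). For two equal groups that differ by d SD, R² = (d²/4)/(1 + d²/4), which is 0.0625/1.0625 = 0.06 at 0.5 SD and 0.16/1.16 = 0.14 at 0.8 SD. With a correlation of 0.5 the change from baseline has variance 2 × (1 − 0.5) = 1, so the same conversion applies to change.

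| Gender effect | Group x Time, no gender term | Single time point, no gender term |
|---|---|---|
| None | 5.0% | 5.1% |
| Constant over time, 0.5 SD | 5.15% | 4.5% |
| Constant over time, 0.8 SD | 5.2% | 3.5% |
| On change, 0.2 SD | 4.9% | 5.0% |
| On change, 0.5 SD | 4.6% | 4.3% |
| On change, 0.8 SD | 3.6% | 3.8% |

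A constant gender difference cancels out of Group x Time but not out of the comparisons at one time point. With gender (and gender x time) in the model, size was 4.95% to 5.4% throughout.

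**Step 3: allocation method and dropout.** With simple randomisation instead of enforced balance, the unadjusted size was 5.1% at R² = 0.10 and at 0.25, so there is no conservatism. With 70 randomised in balance and 54 retained at random, it was about 4.5% at R² = 0.05, 4.1% at 0.10 and about 3% at 0.25.

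**Step 4: power.** If the adjusted test has 80% power (1.96 + 0.84 = 2.80), the unadjusted power is Φ(2.80 − 1.96/√(1 − R²)): Φ(0.79) = 78.5% at R² = 0.05, Φ(0.735) = 76.9% at 0.10 and Φ(0.54) = 70.5% at 0.25. The losses are about 1.5, 3 and 9.5 points.

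Simulated gains depend on a detail. With 27 of each gender, the split within gender is 14 to 13. If the odd participant always falls so that the leftover imbalance favours the unadjusted test, the gain from adding gender looks small: 79.6% to 80.1% at R² = 0.10, 75.5% to 80.4% at 0.25, and 60.3% to 60.9% for Group x Time with 0.8 SD on change. Averaged over both directions (20,000 runs each way), the gains agree with the formula: 77.0% to 80.2% at 0.10 and 69.8% to 79.7% at 0.25. For Group x Time they are 58.4% to 60.4% with 0.5 SD on change and 55.0% to 60.4% with 0.8 SD. With no gender effect, the gender term cost about 0.2 points (60.7% to 60.5%).

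No calculation was made for the Hypothesis 1c path models.

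**The case against.** A reader might infer that the planned tests do run below 5%. The documents do not support that. It needs balance enforced within gender, and no allocation method is stated; it also needs gender to predict the contrast, and no such figure is given. For Group x Time, even a large gender difference leaves the size at about 5% if it is constant over time. These objections stand, and the conclusion has to be conditional.

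The first has limits. Stratifying without enforcing balance would serve no purpose, so balance is the ordinary reading. If balance is not enforced, or dropout disturbs it, a gender term still removes chance imbalance.

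A reader might also infer that a gender main effect never matters because the tests are within-person. That holds for Group x Time but not for the follow-up comparisons at each time point.

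The Protocol (Study Medication) reports no gender differences in suvorexant's effects. This concerns whether the drug works differently in men and women, not whether men and women differ in outcome, so it neither settles the point nor supplies an R². It does fit with leaving out a gender x group term.

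Finally, the error is in the safe direction and the loss is small for weak associations. That also stands and sets the priority. Whether baseline significance tests should be replaced by a descriptive table is a separate reporting matter.

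**Conclusion.** The omission is certain: gender is a randomisation stratum and appears in no outcome model. The consequence is conditional on balance within gender and on gender predicting the analysed contrast. Under both conditions the tests are conservative to the extent tabulated, with size between 5.0% and 2.4% for R² from 0 to 0.25, and somewhat closer to 5% after dropout. The average loss of power is about 1.5 points at R² = 0.05 and 3 points at 0.10. It approaches 10 points only at 0.25, a strong association for which the documents offer no evidence. Gains of 1 point or less at 0.10, and of 3 to 5 points at 0.25, arise when the leftover one-person imbalance favours the unadjusted test. This is a free improvement of low priority. It does not invalidate the planned analysis.

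**What to change.** In the SAP's Data Analysis Plan:

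- Add gender and gender x time, but not gender x group, to the repeated-measures models for Hypotheses 1a and 1b, including the pulse-rate ANOVAs.
- Add gender to the group comparisons at each time point.
- Add gender as a covariate in both equations (mediator and outcome) of each Hypothesis 1c path model.

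It would also help to state how allocation is balanced within gender.

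The cost is one or two sentences and one or two degrees of freedom. With three time points the Group x Time error degrees of freedom fall from (54 − 2) × 2 = 104 to (54 − 3) × 2 = 102. Gender is already recorded for randomisation.

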Clinical interviews. Structured interviews will be conducted by clinically trained staff and will be reviewed weekly in a consensus conference with the candidate (a licensed psychologist) and the primary mentor (a board certified psychiatrist). The CAPS⁵⁵ will be administered to assess current (past month and past week) and lifetime PTSD diagnosis and severity associated with the index trauma. The Structured Clinical Interview for DSM-5 (SCID)⁶² will be administered to assess current and lifetime psychiatric diagnoses and confirm inclusion criteria. The C-SSRS⁶³ will be administered at the initial visit to assess suicidal ideation and behaviors in lifetime and past 6 months and at subsequent visits to assess any changes since the previous visit. The PI will be immediately notified if a participant indicates concerning suicidal ideation or behaviors.

Sleep recordings. PSG recordings in the CRU will use a Natus/Embla (Pleasanton, CA) Titanium PSG unit including two central, frontal, and occipital EEG leads, two electrooculograms, chin and limb electromyograms, and an electrocardiogram. Participants will be instructed to go to bed at their habitual bedtime and wake up at 8 AM. Screening for sleep disordered breathing will be performed using the screening night data. Visual scoring of sleep records will be done following the American Academy of Sleep Medicine Manual, Version 2.3.⁶⁴ We will calculate standard PSG sleep parameters including total sleep time, WASO, the percentage and the duration of each sleep stage, and REM density using the REMLogic software (Natus/ Embla). Sleep changes from baseline to post-WNE will be computed by subtracting baseline measures from respective measures obtained during sleep following the 1st and 3rd WNE sessions.

Alertness visual analogue scale (VAS). Participants will complete an alertness VAS upon awakening in the morning after PSG recordings. The VAS is a 100 mm horizontal line with a label "very sleepy" on the left end and "very alert" on the right end. Participants will be place a

slash mark on the scale to indicate their alertness at the moment. A morning WNE session will not begin until the participant's alertness level reaches the level he/she indicated in the morning after the baseline PSG recording.

Adverse event assessment. Participants will be queried regarding the presence of any symptoms or concerns before and after the medication administration.

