Power considerations. G*Power⁷¹ was used to perform power analysis. $\alpha = .05$ was applied in all analyses. We estimate that 54 participants (27 in each group) will complete protocol (see the Feasibility section). **Hypothesis 1a:** The primary outcomes for power evaluation are WASO and REM sleep. The prior studies suggest small effects of suvorexant on N3; therefore, it was not considered for power evaluation. Herring et al's clinical trials^{48,50} showed that effect sizes of one night of 20/15mg suvorexant on WASO and REM sleep (minutes and %) were $f = -0.37$, 0.32, and 0.22, respectively. A total of 16, 22, and 50 participants are needed to detect a Group x Time effect on WASO and REM sleep in minutes and percentage, respectively, with 80% power. Since no studies have examined effects of suvorexant on PTSD, power analysis for **Hypothesis 1b** is based on effect sizes found in Taylor et al's⁴⁴ clinical trial of prazosin in civilian outpatients with PTSD. 12 participants are needed to detect the effect size found in this trial ($f = 0.40$). **Hypothesis 1c:** Sizes of the indirect effects of suvorexant on PTSD and intersession habituation through post-WNE sleep change are unknown. We selected the bootstrapping procedure as it is more powerful than Sobel test.⁷²

The proposed study also includes comparisons of several other variables. The relative sample size required for multiple comparisons of variables (between 10-20) allowing for Bonferroni-adjusted test to achieve 80% power relative to the sample size required for a nominal is only 3.⁷³ The proposed sample size of 54 will, therefore, have adequate power to detect medium to large effects in our planned analyses. Statistical significance of effects and their clinical importance will be carefully considered in data interpretation to inform the development of subsequent grant applications.

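### Hypothesis 1a, the SAP's primary comparison, is three sleep tests with .05 the only stated alpha and no rule for which decides it; if the drug affected none of the three, the chance of a false positive would be about 12–14%

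*SAP*

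**What the plan says.** The SAP's Data Analysis Plan gives the sleep analysis the leading role: "The primary comparison will be between the 2 groups (suvorexant vs. placebo) and sleep parameters measured at 3 time points". It then plans a separate repeated-measures ANOVA for a "Group x Time interaction effect on each sleep parameter of interest (i.e., N3, WASO, and REM sleep". Per-night follow-up is conditional: "If a significant interaction effect is found, group comparisons will be performed at each time point".

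The SAP's Power considerations section states the level, .05, which "was applied in all analyses". It treats WASO and REM sleep as the primary outcomes for power and gives the totals needed to "detect a Group x Time effect on WASO and REM sleep in minutes and percentage, respectively, with 80% power" as 16, 22 and 50. N3 is left out: "The prior studies suggest small effects of suvorexant on N3; therefore, it was not considered for power evaluation". It nevertheless remains one of the three tested parameters.

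The Protocol's Sleep recordings paragraph says that the software output will include "the percentage and the duration of each sleep stage", so REM and N3 each exist in two forms. The Data Analysis Plan does not say which form is tested.

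Bonferroni appears once, in the closing sizing remark of Power considerations, which concerns further variables. No analysis in the Data Analysis Plan uses it.

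**The concern.** Aim 1 asks whether blocking orexin changes sleep. With three parallel tests and no decision rule, a significant result on any one can be presented as a yes. That includes N3, for which the SAP itself expects little effect. The error rate for that answer is then not the 5% a reader would assume. The SAP says that statistical significance will be weighed, with clinical importance, to inform later grant applications, so a chance finding on one parameter could shape follow-on work. Leaving the form of REM open adds a further choice that could be made after the data are seen.

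**Working it through.** **Inputs from the documents.** Three tests and three time points (SAP, Data Analysis Plan, Hypothesis 1a). Alpha .05; 27 completers per group, 54 in total; effect sizes f = 0.37 (sign dropped) for WASO, 0.32 for REM minutes and 0.22 for REM percent; stated totals of 16, 22 and 50 for 80% power (SAP, Power considerations).

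**Assumptions, not in the documents.** The correlation between sleep parameters; the correlation ρ between repeated measures; and the sphericity factor ε.

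**Step 1: the plan's own figures.** For the within-between interaction with two groups and m time points, power comes from a noncentral F with λ = f²·N·m·ε/(1−ρ), df₁ = (m−1)ε and df₂ = (N−2)(m−1)ε. Totals for 80% power at .05:

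| Setting | WASO | REM min | REM % |
|---|---|---|---|
| SAP | 16 | 22 | 50 |
| m=3, ρ=0.5, ε=1 | 14 | 18 | 36 |
| m=2, ρ=0.5 | 18 | 22 | 44 |
| m=2, ρ=0.45; or m=3, ρ=0.45, ε=0.75 | 18 | 24 | 48 |

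The last row agrees with the SAP to within 2 patients. Because ρ and ε are not stated, the SAP's totals can be neither confirmed nor called wrong. The error rate in step 2 does not depend on them.

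**Step 2: family-wise error when no parameter is affected.**

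- Three independent tests: 1 − 0.95³ = 14.3%.
- Four independent tests (REM in both forms): 1 − 0.95⁴ = 18.5%.

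Simulated null trials (40,000 per setting, 27 per group, 3 time points, each interaction tested at .05):

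| Correlation between parameters | 3 tests | 4 tests |
|---|---|---|
| 0 | 14.2% | 18.7% |
| 0.3 | 13.5% | 17.6% |
| 0.5 | 12.9% | 15.8% |
| 0.7 | 11.2% | 13.4% |

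With REM minutes and REM percent correlated at 0.8–0.9 and the other pairs at 0–0.5, four tests give 14.4–17.2%. I state the three-test result as about 12–14%, rounding the lower end down because the correlations are assumed.

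**Step 3: if some effects are real.** With two parameters unaffected, the chance of a false claim on either is 1 − 0.95² = 9.75% if independent. With only one unaffected it is 5%.

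**Step 4: cost of adjusting.** Holm's strictest step is 0.05/3 = .0167. Three independent tests all at that level give 1 − (1 − .0167)³ = 4.9%. Power at N = 54 and alpha .0167:

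| Setting | WASO | REM min | REM % |
|---|---|---|---|
| m=2, ρ=0.45 | 99.6% | 97.5% | 72.7% |
| m=3, ρ=0.45, ε=0.75 | 99.7% | 98.1% | 73.6% |
| m=3, ρ=0.5, ε=1 | >99.9% | 99.8% | 87.9% |
| m=3, ρ=0.5, ε=0.5 | 98.5% | 94.1% | 62.9% |

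The last row uses λ = f² × 54 × 3 × 0.5/0.5, that is 22.2, 16.6 and 7.8, on 1 and 52 degrees of freedom. It is a harsher setting than the SAP's own sizing implies. N3 has no stated effect size, so its power cannot be computed.

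**The case against.** The strongest reply is that the 12–14% needs a drug with no effect on any of the three parameters. The Protocol's Study Medication section reports that suvorexant reduced WASO and increased REM sleep on the first night. If both effects are real here, only N3 can yield a false positive, at 5%. This stands as a condition on the figure: 12–14% is the rate under a complete null, not a forecast for this trial. It does not supply the missing rule.

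Three source limits also stand. The .05 sits next to the power software in the text, and the Data Analysis Plan states no test level, although no other level appears. The fourth test is inferred from the power section. Fig. 1 could clarify the hypotheses and was not visible.

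Stronger readings that a reader might infer, and that the documents do not support:

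- *Counting every test in Hypotheses 1a to 1c at 5% each makes some chance finding likely.* Bootstrapped indirect effects reject far less often than 5% when both paths are null (about 0.5% in simulation at this size). The SAP also does not fix how many habituation outcomes enter Hypothesis 1c, so no firm count exists.
- *The per-night comparisons inflate the Hypothesis 1a error.* They open only after a significant interaction, so they add nothing to the chance that at least one parameter is declared positive.
- *The Bonferroni remark already covers Hypothesis 1a.* It is a sizing argument about further variables, not a decision rule for N3, WASO or REM.

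**Conclusion.** The point holds for Hypothesis 1a alone. As written, the primary comparison has no single deciding parameter, order or adjustment. If the drug affected none of the three parameters, at least one would be significant in about 12–14% of trials (correlation 0–0.5; about 11% at 0.7), more than twice the nominal 5%. If both REM forms are tested the rate reaches about 18%. This assumes that each test uses .05 and that any one significant parameter is taken as support for Hypothesis 1a; nothing in the visible text prevents either. It is a gap in the decision rule that should be closed. It does not show that a positive result would be false, and it does not make the sample size inadequate.

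**What to change.** In the SAP's Data Analysis Plan, under Hypothesis 1a:

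1. Name one REM measure. REM minutes is the better powered on the SAP's own effect sizes. State the form of N3 as well.
2. Apply Holm across WASO, REM minutes and N3 at a family-wise 0.05: the smallest p-value against .0167, the next against .025 and the last against .05, stopping at the first failure.
3. Report REM percent as an estimate with a 95% interval and no significance claim.

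A fixed sequence of WASO, REM minutes, N3, each at .05, is an alternative. It costs WASO no power, but N3 could be claimed only after both others succeed. That ranking is a scientific choice, since the Protocol's Study Medication section gives weight to slow-wave sleep. Holm avoids it.

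The cost is SAP wording, settled before unblinding, and slightly lower power per test. At the strictest step and 54 completers, power stays at about 99% or more for WASO and about 94–99% for REM minutes, depending on the unstated correlation and sphericity. No change in sample size is needed for those two.

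### The SAP's statement that 54 participants give adequate power in its planned analyses is not supported for the single-night group comparisons that follow a significant interaction under Hypothesis 1a

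*SAP*

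**What the plan says.** The SAP's Data Analysis Plan sets two steps for Hypothesis 1a. Each sleep parameter of interest (N3, WASO, REM sleep) is first tested for a Group x Time interaction over baseline and the two post-session nights. Then: "If a significant interaction effect is found, group comparisons will be performed at each time point". The SAP does not name the test for this second step, any baseline adjustment or multiplicity adjustment, or what the result is for.

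Under Power considerations, alpha = 0.05 "was applied in all analyses", and the number of completers is given as follows: "We estimate that 54 participants (27 in each group) will complete protocol (see the Feasibility section". The effect sizes are f = -0.37 (WASO), 0.32 (REM minutes) and 0.22 (REM percentage). The sample sizes are stated for the interaction: "A total of 16, 22, and 50 participants are needed to detect a Group x Time effect on WASO and REM sleep". The section's closing paragraph concludes: "The proposed sample size of 54 will, therefore, have adequate power to detect medium to large effects in our planned analyses".

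Under Sleep recordings, the Protocol also defines change scores: "Sleep changes from baseline to post-WNE will be computed by subtracting baseline measures from respective measures". The Protocol's design and Study Medication sections set 10 mg for the first administration and 20 mg for the second if the first was well tolerated, so the two treated nights usually differ in dose.

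**The concern.** A two-degree-of-freedom interaction over three time points says only that the group difference is not constant. It does not say on which night the groups differ, or in which direction. For Hypothesis 1a the per-night comparisons are the only written analysis that does, so readers will use them to interpret a significant result. Each compares 27 with 27 on one night. The calculated power does not apply to them, but the general sentence on adequate power includes them.

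At stake is interpretation. If suvorexant has the same effect on both nights, chance alone will often make one night significant and the other not. Because the nights usually differ in dose, such a split could be mistaken for a dose effect, or for no effect at the lower dose.

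**Working it through.** **Inputs.** From the SAP: 27 per group, alpha 0.05, three time points, f = 0.37 (absolute value), 0.32 and 0.22. Assumed because the SAP is silent: two-sided tests, unadjusted two-sample t-tests at each time point, d = 0.5 for a medium and 0.8 for a large effect, and equal correlation rho between nights.

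**The SAP's own figures.** For the interaction, lambda = f² x N x m / (1 - rho), with (m - 1) and (N - 2)(m - 1) degrees of freedom, m being the number of time points. The SAP gives no rho, so 16, 22 and 50 cannot be checked uniquely.
- m = 3, rho = 0.5: N = 14, 18, 36.
- m = 2, rho = 0.5: N = 18, 22, 44.
- m = 3, rho = 0.32: N = 18, 24, 48, each within 2 of the printed value.

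No single setting tried gives all three exactly. The missing correlation is a separate gap.

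**Power of one single-night comparison.** Noncentral t with 52 df, critical value 2.007, noncentrality d x √(27/2) = 3.674d.

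| Effect | d | Noncentrality | Power |
|---|---|---|---|
| Medium (assumed) | 0.50 | 1.837 | 43.8% |
| Large (assumed) | 0.80 | 2.939 | 82.2% |
| 80% threshold | 0.777 | 2.855 | 80.0% |
| WASO, d = 2f | 0.74 | 2.719 | 76.1% |
| REM minutes, d = 2f | 0.64 | 2.352 | 63.6% |
| REM %, d = 2f | 0.44 | 1.617 | 35.5% |

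For d = 0.5, 80% power needs 64 per group (63 gives 79.5%, 64 gives 80.1%), or 128 in total against 54.

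**The other reading of f.** Suppose the group difference is 0 at baseline and d on both treated nights. The interaction effects in each group are then d/3, d/6 and d/6 in size, and f² = (d²/9 + d²/36 + d²/36)/3 = d²/18, so d = f√18. The printed f of 0.22, 0.32 and 0.37 would imply d = 0.93, 1.36 and 1.57. Single-night power is then 92.0%, 99.8% and over 99.9%.

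**Interaction power at the same d = 0.5.** lambda = 54 x 3 x (0.25/18)/(1 - rho) = 2.25/(1 - rho), that is 3.21, 4.50 and 7.50 at rho = 0.3, 0.5 and 0.7. Power is 33%, 45% and 67%.

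**The sequence.** Simulated trials with a true effect of d = 0.5 on both treated nights and none at baseline; pattern among trials with a significant interaction:

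| rho | Both nights significant | Exactly one | Neither |
|---|---|---|---|
| 0.3 | 33% | 50% | 17% |
| 0.5 | 34% | 40% | 26% |
| 0.7 | 34% | 28% | 38% |

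At rho = 0.5, a given treated night is significant in about 54% of these trials. With d = 2f and rho = 0.5, both nights are significant in about 66% (WASO), 53% (REM minutes) and 27% (REM %). At d = 0.93, both are significant in about 87% and neither in 1-3%, for rho from 0.3 to 0.7.

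**The case against.** A reader might infer that the per-night comparisons decide Hypothesis 1a, or that both nights must be significant for it to succeed. The documents do not say so. The interaction is the stated test, the comparisons run only after it is significant, and nothing says a non-significant night overturns it. This part of the objection stands in full.

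A reader might also set the SAP's 80% against 44% as if the follow-up step loses half the power. That mixes effect sizes: 80% refers to the SAP's f values, 44% to d = 0.5. At d = 0.5 and rho = 0.5 the interaction itself has 45% power, so at that effect size the shortfall is not peculiar to the follow-up. This stands too.

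The size of the problem depends on how f is read, and on the interaction reading single-night power exceeds 90%. That also stands, but it does not rescue a general sentence about medium effects unless medium means well above d = 0.5.

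The SAP says only group comparisons, and the Protocol already computes change scores, so unadjusted raw-value tests are an assumption. At d = 0.5 and rho = 0.3, 0.5 and 0.7, single-night change scores give 33%, 44% and 64%, and baseline-adjusted comparisons about 47%, 55% and 71%. None reaches 80%.

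Finally, no passage says that a one-night result will be read as a dose difference, and the SAP promises to weigh clinical importance alongside significance. The misreading is a risk the plan leaves open, not one it commits to. Comparing groups at each time point after a significant interaction is conventional, and power for such follow-ups is seldom stated. The objection here is to the blanket claim that covers them.

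**Conclusion.** The concern holds in a limited form. The SAP claims more power than it calculated. With 27 per group, a single-night comparison has 44% power at d = 0.5, and only effects of about d = 0.78 or more reach 80%. These figures rest on two-sided unadjusted tests and on d = 0.5 as the meaning of medium, which the SAP does not define. For the SAP's planned effects the shortfall is small for WASO, moderate for REM minutes and large for REM % under d = 2f, and absent if f is the interaction f.

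The plan also leaves the role of the follow-up unstated. With equal effects of d = 0.5 on both nights, only about a third of significant interactions would be followed by two significant nights at any of the correlations tried. Significance on one night but not the other is therefore weak evidence of a night or dose difference. The validity of the interaction test is not in question.

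**What to change.** 1. In the SAP's Power considerations, limit the adequate-power sentence to the tests for which power was calculated. Add that single-night group comparisons with 27 per group have 80% power only for d of about 0.78 or more, and 44% at d = 0.5, naming the test assumed.
2. In the Data Analysis Plan for Hypothesis 1a, state that the interaction decides the hypothesis. Report the per-night group differences as estimates with 95% confidence intervals. State that significance on one night but not the other will not be read as a night or dose difference.
3. Optional: prespecify one between-group contrast per sleep parameter, the mean of the two post-session nights against baseline, as a change score or with baseline adjustment. The change score has standard deviation √(1.5(1 - rho)) in units of the single-night SD. At d = 0.5 the standardised effects are 0.488, 0.577 and 0.745, with power 42%, 55% and 77% at rho = 0.3, 0.5 and 0.7, against 33%, 45% and 67% for the interaction. This is better, but still below 80%.

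Items 1 and 2 need only SAP wording, with no new data or participants. The stated power becomes less favourable and the per-night results become descriptive. The optional contrast pools two nights that usually differ in dose.
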